4.5 Sample Size and Statistical Power

Given the lack of established methods for power calculations for the SMLE in our two-stage sampling scheme, we provided minimum detectable effect estimates using the results from a simulation study that we have conducted. The study provides information on the expected efficiency gains of the two-stage SMLE, relative to a standard regression analysis of the Stage II sub-sample only (with complete data on all confounders in addition to exposure and PTD/LBW status). For the purposes of our simulation study, we made a few simplifying assumptions. We assumed three exposure categories: no infection, infection with treatment, infection without treatment, with population prevalence set at 87%, 8% and 5% (similar to preliminary data), and outcome relative risks of 1.0 (ref), 1.5 and 2.0, respectively. We assumed one binary confounder measured in the Stage II sub-sample with varying prevalence across exposure categories and strength of association with outcome. The pregnancy outcome incidence was assumed at 8% (among those unexposed to infection). The Stage I sample size was 90,000, with random selection of 300 in each of the two infection/treatment categories. Relative efficiencies [i.e. $\text{Var}(\text{Stage II MLE}) / \text{Var}(\text{SMLE})$] ranged from 4 to 82 across the scenarios, demonstrating substantial gains by utilizing exposure and outcome information in the full sample of 90,000.

As an approximation to the impact of utilizing exposure and outcome information on 90,000 Stage I women in combination with the Stage II sub-sample of 1200 women, we took an “effective sample size” approach, and assumed the worst case among the simulation scenarios considered, where the relative efficiency of the SMLE was approximately 4.0. Thus, rather than basing power calculations on the Stage II sample size of 600 (300 in each group, for a two-group contrast), we based them on 2400 (i.e. $4.0 * 300$; 1,200 in each cohort category). We acknowledge that estimated gains in efficiency are based on results from a simulation study and may vary in actual analysis.

Power calculations are based on the likelihood ratio test in the context of a Cox proportional hazards regression analysis for PTD, and a logistic regression analysis for LBW, as presented by Self⁵⁸ and as implemented in the software package EGRET⁵⁹. Given previous experience⁶⁰⁻⁶³, we expect negligible loss to follow-up (< 0.20%), a rate of PTD ranging from 8% - 12%⁶⁴, and LBW ranging from 8% to 10%⁶⁵. Each primary contrast of interest in analyses addressing **Aims 1, 2 and 5** can be characterized as a comparison of two groups of women with respect to risk of PTD and LBW. Minimum (maximum, for protective effects) detectable associations are of modest to moderate strength (Table 6). The proposed study will have more than sufficient power to detect the associations observed in our preliminary studies. Relevant to **Aim 3**, we present the maximum (protective effects assumed) detectable pattern of hazard ratios (HR) across cumulative treatment duration categories (no treatment, 1 – 10 days (45% among treated), > 10 days (55% among treated)). For the purpose of detectable effect calculations, we assume a graded, linear trend in (log) hazard/odds ratios across duration categories, a two-sided test for trend and a significance level of .05. We have sufficient power (.80) to detect a pattern of PTD HRs of 1.0 (ref), .82, and .67 associated with no treatment, 1-10 days and >10 days, respectively, assuming the worst case

scenario of expected 8% PTD rate. Similarly, we have sufficient power (.80) to detect a pattern of

Table 6. Minimum (maximum for protective scenarios) detectable hazard ratios (HR) for preterm delivery and detectable odds ratios (OR) for low birthweight in pair-wise comparisons of genital herpes exposure/treatment categories; two-sided test, significance level (α) = .05, power (1- β) =.80.

Contrast	Preterm Delivery (HR)		Low Birthweight (OR)	
	Rate = 8%	Rate = 11%	Rate = 8%	Rate = 10%
Treated infection vs. untreated infection (Aim 1; A+ B vs. C)	.71	.75	.70	.72
Treated < 3 rd trimester vs. 3 rd trimester (Aim 2, A vs. B)	.66	.71	.65	.68
Untreated infection vs. no infection (Aim 5, C vs. D)	1.51	1.40	1.54	1.47

odds ratios ORs of 1.0 (ref), .81, and .66 associated with no treatment, 1-10 days and >10 days, respectively, assuming the worst case scenario of expected 8% LBW rate.

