4.2 Estimation

Regression parameter estimates and associated standard errors will be obtained via semiparametric maximum likelihood (SMLE)⁵⁰ utilizing exposure, outcome, and confounder measurements on all 90,000 Stage I units in addition to the additional confounder/effect modifier measurements on the subset sample at Stage II. Thus, our study design can be characterized as a missing data problem, with Stage II covariates only assessed on a subset of the full cohort. Scott and Wild presented a unified method for fitting arbitrary regression models to a large class of missing data and/or response selective sampling problems. These applications are generally characterized as: 1) a set of easily-obtainable variables are measured on a sample of N individuals (Stage I); one or more of these variables are to be used as explanatory in the regression model (e.g. herpes and treatment status), or are informative surrogates for “expensive” variables to be measured on a subsample; 2) the response variable is obtained for all N individuals (e.g. LBW and PTD status) or a subset; and, 3) a set of “expensive” explanatory variables (e.g. details in genital herpes history and characteristic, compliance to treatment, and potential confounders/effect modifiers) are measured on a subsample (Stage II). Parameter estimation is by maximizing the profile likelihood (R software available from the authors), with the estimator shown to be consistent and have full semiparametric efficiency⁵⁰.

Aim 1. Does treating genital herpes infection in pregnant women reduce the risk of adverse pregnancy outcomes including PTD or LBW? (treated vs. untreated)

Point and interval estimates of the hazard ratio for PTD associated with treated genital herpes vs. not treated infection, will be calculated as described above, using Cox regression (Cohort A + B vs. C). In determining potential confounders in our regression models, we will first examine

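### Table 6 leaves out the variance cost of confounder adjustment: at the plan's own worst-case efficiency of about 4.0, power at the printed limits for the simulated contrasts is about .68 to .71, not .80

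*Combined protocol and SAP*

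**What the plan says.** Section 4.2 plans to estimate the regression parameters by SMLE, using Stage I data on all 90,000 women and the extra Stage II confounders on the interviewed subset. The analysis to be reported is therefore adjusted for Stage II variables.

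Section 4.5 defines relative efficiency (RE) as Var(Stage II MLE)/Var(SMLE). The Stage II analysis in the numerator is one "with complete data on all confounders in addition to exposure and PTD/LBW status". In the sponsor's simulation RE "ranged from 4 to 82 across the scenarios". The plan "assumed the worst case among the simulation scenarios considered, where the relative efficiency of the SMLE was approximately 4.0", multiplied 300 by that value, and based power on "1,200 in each cohort category".

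Each contrast for Aims 1, 2 and 5, it then says, "can be characterized as a comparison of two groups of women with respect to risk of PTD and LBW". Table 6 gives detectable effects for a "two-sided test, significance level (α) = .05, power (1- β) =.80". Section 4.5 mentions no covariate, R-squared or variance-inflation term.

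**The concern.** An efficiency ratio is tied to its reference variance. Here the reference is the adjusted Stage II variance, so Var(SMLE) = Var(adjusted Stage II)/4.0. Entering 4.0 x 300 women into an unadjusted formula instead assumes Var(SMLE) = Var(unadjusted Stage II)/4.0, which is smaller. If VIF = Var(adjusted Stage II)/Var(unadjusted Stage II), the equivalent unadjusted size per cohort is 300 x RE/VIF, not 300 x RE.

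The VIF cannot be close to 1 in the scenario chosen. Without confounding, RE would be far above 4. It falls to 4 because adjustment adds variance that only the Stage II women can resolve, and that same variance inflates the Stage II regression.

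At stake is how a null result is read. Table 6 is offered as a conservative statement of what the study can detect with .80 power, and it is not conservative at the efficiency on which it is built.

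**Working it through.** **Inputs.** From section 4.5: two-sided alpha .05, power .80, RE 4.0, 1,200 per cohort, PTD rates 8% and 11%, LBW rates 8% and 10%. Simulation: N = 90,000; shares 87/8/5% (uninfected, treated, untreated); baseline risk 8%; relative risks 1.0/1.5/2.0; 300 sampled in each infected category; one binary confounder. Assumed: the confounder's prevalences and odds ratio, and 300 uninfected women in Stage II.

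**1. Reproduce Table 6 with no covariate term.** For PTD, the detectable HR is exp(±2.802/√(events x f)), where 2.802 = 1.960 + 0.842 and f is the product of the two group fractions. Aim 1 is 2,400 vs 1,200 (f = 2/9); Aims 2 and 5 are 1,200 vs 1,200 (f = 1/4). For example, Aim 1 at 8% has 3,600 x .08 = 288 events, 288 x 2/9 = 64, and exp(-2.802/8) = .705. LBW uses the two-group binomial likelihood ratio.

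| Contrast | PTD recomputed | PTD printed | LBW recomputed | LBW printed |
|---|---|---|---|---|
| Aim 1 | .705/.742 | .71/.75 | .701/.724 | .70/.72 |
| Aim 2 | .667/.708 | .66/.71 | .654/.681 | .65/.68 |
| Aim 5 | 1.498/1.412 | 1.51/1.40 | 1.530/1.468 | 1.54/1.47 |

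Every cell agrees to within about .015, so the table contains no adjustment cost.

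**2. VIF implied by RE = 4.0, closed form.** Let M be the ratio of Stage I to Stage II information for the unadjusted contrast. Approximately, Var(SMLE) = Var(unadjusted Stage II) x [(VIF - 1) + 1/M], so RE = VIF/[(VIF - 1) + 1/M]. Setting RE = 4 gives VIF = (4/3)(1 - 1/M).

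- Treated vs untreated: group sizes are 7,200 and 4,500 in Stage I, 300 each in Stage II; risks are 12% and 16%. The variance is 1/(7,200 x .1056) + 1/(4,500 x .1344) = .00297 in Stage I and 1/(300 x .1056) + 1/(300 x .1344) = .0564 in Stage II. M is about 19 and VIF about 1.26.
- Untreated vs uninfected: 4,500 and 78,300 in Stage I; risks 16% and 8%. The variances are .00183 and .0701. M is about 38 and VIF about 1.30.

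**3. VIF by exact information matrices.** The expected information for the unadjusted Stage II, adjusted Stage II and two-stage estimators was computed on the inputs above, over assumed confounder prevalences of .05 to .80 in each category and odds ratios of 1.5 to 8. In all scenarios with RE between 3.8 and 4.2, VIF was 1.24 to 1.29 (treated vs untreated) and 1.28 to 1.32 (untreated vs uninfected). None came near 1.

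**4. Power at the .80 limits.** Power = Φ(2.802/√VIF - 1.960), and the equivalent size is 1,200/VIF.

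| VIF | Equivalent n per cohort | Power |
|---|---|---|
| 1.25 | 960 | .707 |
| 1.26 | 952 | .704 |
| 1.30 | 923 | .690 |
| 1.32 | 909 | .684 |

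**5. Where the shortfall ends.** From step 2, RE/VIF = (RE - 1)/(1 - 1/M). It reaches the 4 that Table 6 needs at RE = 1 + 4(1 - 1/M): 4.79 for M = 19, 4.89 for M = 38, and 5 as M grows without limit. At RE = 6 power is about .89, and at RE = 8 about .96.

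**The case against.** The strongest reply concerns scope. The plan used the lowest RE in a range reaching 82, called the step an approximation, noted that no established power method exists for this estimator, and warned that the gains may vary. An RE near 4 also requires substantial confounder imbalance. The extra confounders that section 3.3.3 names (multivitamin intake, physical activity) are not obviously that unbalanced. All of this stands as a limit on reach. The caveat does not remove the point, though: it concerns uncertainty in the 4.0, and the mismatch remains when 4.0 is exactly right.

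The simulation also cannot be fully reproduced. Its confounder inputs are not given, and the no-confounding ceilings from the stated inputs (about 19 and 38 for these contrasts, about 50 at most) lie below the reported 82. The VIF is therefore back-calculated. The direction is secure: even M = 82 gives (4/3)(1 - 1/82) = 1.32.

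Three stronger readings are tempting, and the documents do not support them:

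- *The planned analysis has about .70 power.* That holds only at an RE of about 4; most of the reported range is unaffected.
- *All twelve Table 6 cells fall to .70, and corrected limits can be written in by hand.* The simulation had one treated category, so it contained no early-versus-late contrast, and the single worst RE is not tied to a contrast. Its shares also differ from section 3.3.3, which expects 4,200 treated and 6,600 untreated women (4.7% and 7.3% of 90,000) against the simulated 8% and 5%. With the planned sizes and a VIF of 1.26 to 1.33, the same approximation gives roughly .59 to .67 for Aim 1 and .65 to .75 for Aim 5, so the figure does not carry over unchanged.
- *The preliminary effects become undetectable.* The PTD odds ratios of 0.49 and 2.23 and the treated-versus-untreated LBW odds ratio of 0.60 remain well beyond any plausible corrected limit. The untreated-infection LBW odds ratio of 1.45 is already weaker than the printed 1.54/1.47, so that gap has another cause.

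**Conclusion.** The point holds at the plan's own worst case. Section 4.5 applies an efficiency defined against an adjusted analysis to an unadjusted sample size, and Table 6 omits the cost of adjustment. At RE of about 4.0, power at the printed limits for the two simulated contrasts is about .68 to .71 instead of .80, and the equivalent size is roughly 910 to 960 per cohort instead of 1,200. At RE of about 5 or more the stated .80 is met.

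This rests on the simulation inputs in section 4.5, one binary confounder with assumed prevalences and strength, 300 uninfected women in Stage II, a logistic approximation for the Cox analysis, and RE = 4.0 applying to each simulated contrast. For Aim 2, and for the Aim 3 patterns if they use the same effective size, only the direction is established. The power statement should be corrected; neither the design nor the preliminary case for the study is overturned.

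**What to change.** Recompute Table 6 and the Aim 3 patterns directly from the simulated Var(SMLE) in the worst-case scenario, with noncentrality (log HR or log OR)²/Var(SMLE). Do this contrast by contrast, adding the early-versus-late treatment contrast for Aim 2, and at the cohort sizes expected in section 3.3.3 (2,100, 2,100, 6,600 and 79,200). If the effective-size device is kept, use 300 x RE/VIF, taking both quantities from the same scenario and contrast.

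Report that scenario's confounder prevalences, its strength of association with outcome and the VIF. Then either restate the detectable HRs and ORs at .80 power or state the power at the printed values.

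The cost is a rerun, with the added contrast and planned sizes, of a simulation the sponsor reports having conducted, plus revised wording in section 4.5. Enrolment does not change. The only downside is slightly less favourable stated limits.

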Genital tract infections, including genital herpes infection, have long been suspected to be important risk factors for PTD and LBW¹²⁻²². The emerging literature linking placental inflammation as a common culprit and pathway triggering early labor onset resulting in PTD and LBW has provided a further supporting mechanism for genital tract infection as an important risk factors for adverse pregnancy outcomes¹²⁻¹⁶. Among the infectious agents, genital herpes infection has emerged as an important modifiable risk factor for adverse pregnancy outcomes, both (1) because genital herpes infection is quite prevalent among pregnant women, and (2) because treating genital herpes infection in pregnant women has been effective²³ and emerging evidence has demonstrated that treating pregnant women with genital herpes infection may lead to significant reduction of PTD and LBW²¹.

Genital herpes, a sexually transmitted disease due to infection by the herpes simplex virus (HSV)²⁴, is prevalent among pregnant women. The prevalence based on seropositivity is estimated at around 10-15% in the U.S. although a large of proportion of those may be asymptomatic²⁴⁻³⁰. Genital herpes infection, if untreated during pregnancy, has been associated with increased risk of adverse pregnancy outcomes including PTD, LBW and miscarriage both for symptomatic and asymptomatic genital herpes infection^{17-22,31-35}. Our preliminary results have provided additional evidence that genital herpes infection, if not treated before the 3rd trimester, is associated with a more than two-fold increased risk of **PTD** (odds ratio (OR)=**2.23**, 95% confidence interval (CI)=1.80-2.76) and a 45% increased risk of **LBW** independent of PTD: OR=**1.45**, 95%CI=1.07-1.97 (Table 1). Thus, genital herpes infection is an important contributor to adverse pregnancy outcomes due to its prevalence in pregnant women, and likely to have been overlooked in the search for risk factors and prevention strategies to reduce PTD and LBW to improve pregnancy outcomes and newborn health^{21,35}.

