risk factors that may be plausibly linked to infection and PTD. Inclusion or exclusion of potential confounding factors in our final regression models will be evaluated based on comparison of the regression coefficient associated with the contrast of interest (treated vs. untreated) both adjusted and unadjusted for the potential confounder under consideration (i.e. inclusion if regression coefficient changes by 10% or more). The change-in-estimate approach to confounder selection performs well with regard to power, bias, mean squared error and confidence interval coverage for the primary factor of interest⁴⁵. Continuous potential confounders will first be categorized either as quartiles, or into clinically relevant categories (e.g. BMI classification, amount of cigarette smoked or alcohol intake). The shape of the association/pattern of regression coefficients across increasing levels of the categorized covariate, of interest in their own right, will serve as a guide in the approach to modeling the variable as a continuous independent variable. A simple linear term may be appropriate, but higher order polynomial terms may be necessary to capture any non-linearity in association. Departures from model assumptions will be assessed via diagnostic plots of weighted residuals and tests for interaction between exposure and time (gestational age).

Analyses of LBW as the outcome will parallel those described above for PTD, but logistic regression techniques will be used rather than Cox regression, in Aims 1 – 5.

Aim 2. Does the timing of the treatment during pregnancy influence the treatment effectiveness on reducing adverse pregnancy outcomes (PTD and LBW)? (A head-to-head comparison of treatment timing: before the 3rd trimester vs. during the 3rd trimester).

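### Section 4.5 claims ample power for all preliminary associations, but the LBW odds ratio of 1.45 falls below both Aim 5 limits in Table 6 (1.54 and 1.47)

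*Combined protocol and SAP*

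**What the plan says.** Section 4.5 sizes each contrast by an effective-sample-size argument. The simulated efficiency of the two-stage estimator, relative to an analysis of Stage II alone, "ranged from 4 to 82 across the scenarios". For Table 6 the authors "assumed the worst case among the simulation scenarios considered, where the relative efficiency of the SMLE was approximately 4.0", which turns 300 interviewed women per cohort into 1,200. They add a caveat: "We acknowledge that estimated gains in efficiency are based on results from a simulation study and may vary in actual analysis".

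Table 6 then gives detectable effects at 80% power and two-sided 0.05. In the row "Untreated infection vs. no infection (Aim 5, C vs. D)" the LBW odds ratios are 1.54 at an 8% rate and 1.47 at a 10% rate. The text that introduces the table concludes: "The proposed study will have more than sufficient power to detect the associations observed in our preliminary studies".

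The preliminary associations are in section 1. Part A.2 says that "genital herpes infection, if not treated before the 3rd trimester, is associated with a more than two-fold increased risk of" PTD (OR 2.23) and gives the LBW result as "independent of PTD: OR=1.45, 95%CI=1.07-1.97". Part A.3 restates these as untreated infection compared with controls, and adds treated vs untreated ORs of 0.49 for PTD and 0.60 for LBW. On the planned LBW analysis, section 4.2 says: "Analyses of LBW as the outcome will parallel those described above for PTD", with logistic regression in place of Cox regression. No adjustment for PTD, or restriction by it, is mentioned.

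**The concern.** The power sentence is the only place where the plan links its detectable effects to the effects it expects. A reader would take it that every preliminary association clears 80% power in Table 6, with room to spare. For Aim 5, which section 4.5 lists among the primary contrasts, the printed LBW estimate does not clear either column, so it falls short over the whole 8-10% LBW range that the plan assumes. If the Aim 5 LBW result came out null, a reader relying on this sentence would credit the comparison with more power at the preliminary effect size than the table supports.

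**Working it through.** **Inputs.** Two-sided alpha 0.05, power 0.80, 1,200 vs 1,200 at efficiency 4.0, LBW 8% or 10%, Table 6 limits (all section 4.5). Preliminary ORs 2.23, 1.45, 0.49 and 0.60 (section 1, A.2 and A.3).

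**Step 1: reproduce Table 6.** I computed likelihood ratio test power for two binomial groups of 1,200, reading the tabulated rate as the overall rate across both groups. The smallest detectable ORs are 1.53 (8%) and 1.47 (10%), against the printed 1.54 and 1.47. Reading the rate as that of the reference group gives 1.48 and 1.43, which does not reproduce the table. The overall-rate reading is therefore used below.

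**Step 2: compare each preliminary estimate with its row.**

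| Preliminary estimate | Table 6 row | Limits (lower rate, higher rate) | Clears? |
|---|---|---|---|
| PTD 2.23 | Aim 5 | 1.51, 1.40 | yes |
| PTD 0.49 | Aim 1 | .71, .75 | yes |
| LBW 0.60 | Aim 1 | .70, .72 | yes |
| LBW 1.45 | Aim 5 | 1.54, 1.47 | no, in either column |

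The PTD estimates are odds ratios set against hazard ratio limits. As risk ratios at 8% they are about 2.03 and 0.51-0.53, so the conclusion is the same.

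**Step 3: power implied by Table 6.** A limit at 80% power implies SE = ln(limit) / (1.960 + 0.842) = ln(limit) / 2.802. Power at an estimate is then Phi(|ln OR| / SE - 1.96).

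- 8%: SE = 0.4318 / 2.802 = 0.1541. Power at 1.45 = Phi(0.3716 / 0.1541 - 1.96) = Phi(0.451) = 0.674.
- 10%: SE = 0.3853 / 2.802 = 0.1375. Power at 1.45 = Phi(0.3716 / 0.1375 - 1.96) = Phi(0.742) = 0.771.
- Other three: PTD 2.23 and PTD 0.49 above 0.999; LBW 0.60 gives 0.980 and 0.992.

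The direct likelihood ratio calculation at OR 1.45 gives 0.689 (8%) and 0.774 (10%).

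**Step 4: efficiency needed for 80% power at 1.45.** Variance scales as 1/efficiency, so the requirement is 4 x (ln limit / ln 1.45)^2.

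- 8%: 4 x (0.4318 / 0.3716)^2 = 5.40 (direct calculation 5.22).
- 10%: 4 x (0.3853 / 0.3716)^2 = 4.30 (direct calculation 4.26).

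| Relative efficiency | Power at 8% LBW | Power at 10% LBW |
|---|---|---|
| 4.0 | 0.67-0.69 | 0.77 |
| 6 | 0.84-0.85 | 0.91 |
| 10 | 0.97 | 0.99 |

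**Step 5: what an overall-LBW odds ratio might be.** This step rests on assumptions that are not in the documents: OR 1.45 holds within both preterm and term births, the PTD OR is 2.23, reference PTD is 8-12%, and LBW risk among reference preterm births is 15-60%. The term LBW risk is solved so that reference LBW equals 8% or 10%. Exposed PTD follows from the OR of 2.23, and 1.45 is applied in each stratum. The implied overall-LBW OR is 1.57-2.35 at 8% and 1.52-2.17 at 10%. Power at the two minima, at efficiency 4.0, is 0.83 and 0.86.

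**The case against.** The strongest reply is that 1.45 is not the effect the Aim 5 LBW cells are sized for. It is independent of PTD, whereas the planned LBW analysis states no conditioning on PTD. In every scenario of step 5 the overall-LBW OR clears Table 6 even at efficiency 4.0. This stands as a reason not to call the study underpowered. It does not rescue the sentence, because the text supplied gives no overall-LBW estimate, and the preliminary Tables 1 and 2, which might contain one, are not in it.

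Second, the preliminary group may include women treated in the 3rd trimester, which is closer to B+C vs D. With 2,400 vs 1,200 at efficiency 4.0, power at 1.45 would be 0.78 at 8% and 0.86 at 10%. That removes the shortfall at 10% but not at 8%. Table 6 has no such row, and A.3 itself presents the result as untreated vs controls.

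Third, 4.0 is the floor of the simulated range, and an effect just inside a worst-case bound does not contradict a claim about the study as run. That is fair, and a modest rise in efficiency restores 80%. But the plan chose 4.0 as the basis of its table and gives no higher value for C vs D. Its caveat that gains may vary is not carried to the power sentence and does not exempt this association.

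Finally, on the reference-group reading of the rate, power would be 0.76 and 0.83. That is still short at 8%, and the reading does not match the table.

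**Conclusion.** The concern holds, as a minor point. The sentence is broader than the table behind it: three of the four printed preliminary associations are supported, and the Aim 5 LBW OR of 1.45 is not. At the plan's own efficiency of 4.0, power there is 67-69% at 8% LBW and 77% at 10%.

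These are the lowest figures within the simulated efficiency range. They treat 1.45 as the C vs D effect, which is only an approximate match. The comparison of 1.45 with 1.54 and 1.47 is certain. Whether the study actually lacks power for Aim 5 LBW is not established and, under the assumptions of step 5, would not be the case. The consequence is confined to how the Aim 5 LBW power statement is read.

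**What to change.** Make one of three changes in section 4.5.

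- **Limit the claim.** Suggested text: At the worst-case relative efficiency of 4.0, Table 6 supports more than 80% power for the preliminary PTD associations (2.23 and 0.49) and the treated vs untreated LBW association (0.60). For Aim 5 LBW, power at an OR of 1.45 is about 67-69% at 8% LBW and 77% at 10%; 80% is reached at a relative efficiency of about 5.4 and 4.3 respectively.
- **Name the matching estimate.** Keep the sentence and cite the preliminary overall-LBW estimate that corresponds to C vs D, provided it clears 1.54 and 1.47.
- **Recompute the row.** Keep the sentence and recalculate C vs D with a relative efficiency justified for that contrast, using Cohort D's expected 79,200 women (section 3.3.3).

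The cost is one sentence or one table row. Enrolment, analysis and estimates do not change.
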